3.1. INCLUSION CRITERIA

Study participants meeting all of the following criteria will be allowed to enroll in the study:

1. Males and females ages 18 to 65 years old, inclusive, at the Screening Visit
2. Clinical diagnosis of primary or secondary progressive MS (PPMS or SPMS) based on the 2017 revised MacDonald Criteria and have confirmation by the Investigator that the disease has entered the progressive stage at least 6 months prior to enrollment.
3. No evidence of clinical MS relapse or high dose pulse corticosteroid treatment within 6 months prior to screening.
4. Disability status at screening with an Expanded Disability Status Scale (EDSS) 3.0-6.5, inclusive
5. Able to walk 25 feet in 60 seconds or less
6. Stable dose of non-excluded MS Disease Modifying Therapy for at least 6 months prior to Screening Visit (Visit 1).
7. Women of childbearing potential shall either be surgically sterile, or must agree not to become pregnant for the duration of the study. Women must be willing to undergo a serum pregnancy test at screening, and at the conclusion of the study. Participants of childbearing potential must agree to use a medically approved form of birth control (abstinence, intrauterine device (IUD), oral contraception, barrier and spermicide or hormonal implant) throughout the duration of the study and for at least 3 months following the last transplantation. For those women who are sexually active and using oral contraceptives, a second form of barrier contraception is required. Men must be willing to consistently use two forms of contraceptive if their partners are of childbearing age.
8. Capable of providing informed consent and willing and able to follow study procedures, including willingness to undergo multiple/repeated lumbar puncture.

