2.4. DURATION OF STUDY

Participants will be screened and eligible participants will be enrolled and will undergo viral safety testing within 7 days of the scheduled Bone Marrow Aspiration (BMA).

Following aspiration, MSC will be isolated, propagated for about 2 weeks and cryopreserved. About 2 weeks prior to each treatment, MSC will be thawed, propagated and induced into MSC-NTF cells. Participants will undergo IT administration of NurOwn® (MSC-NTF cells) on Day 0 (Visit 3), Week 8 (Visit 4) and Week 16 (Visit 5). Following each cell transplantation, participants will be monitored as inpatients for a period of up to 24 hours. Participants will be discharged after up to 24 hours unless a clinical AE(s) occurs and requires continued inpatient monitoring and/or treatment. After the last dose, participants will be followed for approximately 12 weeks for efficacy and safety assessment. Each subject's participation in the study will last for approximately 38 weeks.

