10. Current use of immunosuppressant medication or use of such medication within 6 months of study enrollment (aside from Rituximab or other approved B-cell immunotherapy). Alemtuzumab (Lemtrada), Cladribine (NDA submitted), Natalizumab (Tysabri), S1P modulators (Gilenya) are excluded for safety reasons due to the known risk of systemic autoimmune disease, malignancy, opportunistic infections, and cardiovascular toxicity associated with these therapies, as well as theoretical effects on MSC-NTF cell homing and migration, that may be associated with Natalizumab and/or S1P modulators (Gilenya).
11. Any history of acquired or inherited immune deficiency syndrome.
12. Any history of either substance abuse within the past year, or unstable psychiatric disease according to the Investigator's judgment.
13. Pregnant women or women currently breastfeeding.
14. Subjects for whom MRI is contraindicated (i.e., have a pacemaker or other metallic implanted device, or are unable to remain in the machine for period of time needed to acquire a scan).

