4.6. PRE-TRANSPLANTATION VISITS

4.6.1. Visit 1: Screening Visit

Visit 1 is the Screening Visit and precedes Visit 2 by up to 4 weeks

Participants will undergo the following screening assessments:

- Informed consent (to be obtained by the Principal Investigator [PI] or Sub-Investigator [Sub-I])
- Determine study eligibility, review of Inclusion/Exclusion Criteria
- Collect demographic data
- Medical history
- Medical history of MS symptoms and date of diagnosis
- Standard 12-Lead ECG
- Neurological examination
- Review of prior concomitant medications
- Review of adverse events (AEs)
- Directed physical examination, including height and weight
- Vital sign measurements (including blood pressure, body temperature; pulse and respiration rate after sitting for at least 3 minutes)
- Blood collection for hepatitis B virus (HBV; surface antigen (HBsAg) and antibodies to core antigen (IgG and IgM anti-HBc), hepatitis C virus (HCV), human immune deficiency virus (HIV) 1 and 2. These tests must be performed within 7 days of Bone Marrow aspiration, and must be repeated if Bone Marrow aspiration is scheduled more than 7 days after the

Brainstorm Cell Therapeutics Ltd.	IND#018615	
Phase 2 Clinical Protocol BCT-101-US Amendment 1.1, June 2019	MSC-NTF cells (NurOwn®)	Page 28 of 59

Screening visit. Viral safety tests must be performed by CLIA certified laboratories using Food and Drug Administration (FDA) cleared kits.

- Blood collection for hematology (CBC (hematology panel) - hemoglobin, hematocrit, white count (and differential), platelet count), coagulation (PT, PTT, INR), biochemistry evaluations (Sodium, potassium, chloride, glucose, BUN, creatinine, bicarbonate, calcium, total bilirubin, AST, ALT, ALP, uric acid, total cholesterol, HDL, LDL)
- Blood collection for a serum pregnancy test (Female participants of childbearing potential)
- Urinalysis (Specific gravity, pH, glucose, protein, ketones, blood)
- Columbia-Suicide Severity Rating Scale (C-SSRS baseline)
- MS functional composite (MSFC): T25FW and 9HPT
- EDSS
- MSWS-12
- LCLA
- SDMT
- MRI
- For eligible subjects: issue wearable sensor device and train on timing of use as well as maintenance of device

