4.7. TRANSPLANTATION VISITS

4.7.1. Visit 3 (T1): 1st Cell Transplantation (Day 0- up to Day 1)

At the first transplantation visit, approximately 5-6 weeks from BMA (coordinated with patient-assigned manufacturing slots) participants will be admitted to an inpatient study unit for study procedures (See Table 1 and Table 2).

Pre-transplant assessments (Up to 8 hours before transplant) will include:

- Admission to Inpatient facility
- Directed physical examination
- Vital sign measurements (including blood pressure, body temperature; pulse and respiration rate after sitting for at least 3 minutes)
- Review of concomitant medications
- Review of adverse events
- Blood will be collected for hematology (CBC (hematology panel), coagulation (PT, PTT, INR), biochemistry (sodium, potassium, chloride, glucose, BUN, creatinine), and biomarker evaluations. Hematology, coagulation and chemistry lab results will be reviewed prior to the lumbar puncture.
- MS functional composite (MSFC): T25FW and 9HPT
- EDSS
- MSWS-12
- LCLA
- SDMT

Following pre-transplant procedures participants will undergo a lumbar puncture:

- CSF will be removed and retained for analysis immediately prior to the IT administration of cells
- MSC-NTF cells will be administered IT

Post-transplant, participants will undergo the following:

- Vital signs will be monitored at 2 (\pm 15 minutes), 8 (\pm 15 minutes) and 20 hours (\pm 30 minutes) post-transplantation.
- Visual inspection of the injection site will be performed at 2 (\pm 15 minutes), and 20 (\pm 30 minutes) hours post-transplant.
- Blood will be collected 20 hours (\pm 30 minutes) post-transplant for biomarker evaluations.

Prior to discharge at approximately 24 hours post transplantation, assessments will include:

Brainstorm Cell Therapeutics Ltd.	IND#018615	
Phase 2 Clinical Protocol BCT-101-US Amendment 1.1, June 2019	MSC-NTF cells (NurOwn®)	Page 30 of 59

- Vital sign measurements (including blood pressure, body temperature; pulse and respiration rate after sitting for at least 3 minutes)
- Directed physical examinations
- Review of concomitant medications
- Review of adverse events

Patient will then be discharged from Inpatient Study facility

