4.8.3. Visit 7: Week 28 (\pm 5 days) Follow-Up

At week 28 post transplantation follow-up, all participants will undergo:

- Review of concomitant medications
- Review of adverse events
- Vital sign measurements (including blood pressure, body temperature; pulse and respiration rate after sitting for at least 3 minutes)
- Directed physical examination, including weight
- Neurological examination
- Blood collection for hematology (CBC (hematology panel) - hemoglobin, hematocrit, white count (and differential), platelet count), coagulation (PT, PTT, INR), biochemistry evaluations (Sodium, potassium, chloride, glucose, BUN, creatinine, bicarbonate, calcium, total bilirubin, AST, ALT, alkaline phosphatase, uric acid, total cholesterol, HDL, LDL)
- Blood collection for a serum pregnancy test (Female participants)
- Urinalysis (Specific gravity, pH, glucose, protein, ketones, blood)
- MS functional composite (MSFC): T25FW and 9HPT
- EDSS
- MSWS-12
- LCLA
- SDMT

Brainstorm Cell Therapeutics Ltd.	IND#018615	
Phase 2 Clinical Protocol BCT-101-US Amendment 1.1, June 2019	MSC-NTF cells (NurOwn®)	Page 34 of 59

- C-SSRS
- MRI
- Return wearable sensor device

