15. APPENDICES

15.1. APPENDIX 1: LISTING OF STUDY ACTIVITIES

15.1.1. *Scheduled monitoring events*

The schedule of assessments table provides an overview of the protocol visits and procedures. Refer to the Study Assessments section of the protocol for detailed information on each procedure and assessment required for compliance with the protocol.

Unscheduled visits may be required in the course of the study in addition to those listed.

Brainstorm Cell Therapeutics Ltd.	IND#018615	
Phase 2 Clinical Protocol BCT-101-US Amendment 1.1, June 2019	MSC-NTF cells (NurOwn®)	Page 52 of 59

Table 1. Schedule of Assessments:

Study Period	Pre-treatment period		Cells Transplantation period					Post-transplantation follow-up		
	V1	V2	V3	V3T	V4	V4T	V5	V5T	V6	V7 ¹¹
Visit										
Procedure	Screening/ Enrollment	BMA	Cell Transplantation (T1)	Telephone Call visit	Cell Transplantation (T2)	Telephone Call visit	Cell Transplantation (T3)	Telephone Call visit	Follow-up visit	End of Study Visit
Time Schedule	Week -10-6 [*]	Week -5 to -6	Day 0 - Day 1 ¹²	Week 1-2	Week 8 (± 14 days) ¹²	Week 9-10	Week 16 (± 14 days) ¹²	Week 17-18	Week 22 (± 5 days)	Week 28 (± 5 days)
Informed consent	√									
Eligibility criteria	√									
Demographic data	√									
Height	√									
Medical History	√									
MS Medical History ¹	√									
12 lead ECG	√									
Neurological Examination	√									√
Viral safety testing (HIV 1 and 2, HBV and HCV)**	√									
Body weight	√									√
Pregnancy test (for women with childbearing potential)	√									√
Bone marrow aspiration		√								
Transplant (IT)			√		√		√			
CSF collection			√		√		√			
Visual inspection of injection site			√		√		√			
Blood collection for biomarkers			√		√		√		√	
Physical examination	√		√		√		√		√	√
Vital signs ²	√	√	√		√		√		√	√
Hematology ³	√	√	√		√		√			√
Blood biochemistry ⁴	√		√		√		√			√
Coagulation tests ⁵	√	√	√		√		√			√
Prior/Concomitant medication review	√	√	√	√	√	√	√	√	√	√
Adverse events review	√	√	√	√	√	√	√	√	√	√
Urinalysis ⁶	√									√
EDSS ⁷	√		√		√		√		√	√
C-SSRS	√									√
MRI	√									√
Low Contrast Letter Acuity (LCLA)	√		√		√		√		√	√
MS functional composite ⁸	√		√		√		√		√	√
SDMT ⁹	√		√		√		√		√	√
MSWS-12 ¹⁰	√		√		√		√		√	√
Wearable sensor device issued and training	√									
Wearable sensor device	√	√	√	√	√	√	√	√	√	√

Brainstorm Cell Therapeutics Ltd.	IND#018615	
Phase 2 Clinical Protocol BCT-101-US Amendment 1.1, June 2019	MSC-NTF cells (NurOwn®)	Page 53 of 59

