1 MS Medical History to collect type and duration of MS symptoms and Date of Diagnosis

2 Pulse rate, Blood pressure (Respiratory rate, Body temperature)

3 Hematology: Complete blood count (red blood cells with indices, white blood cells with differential and platelet count, hemoglobin, hematocrit)

4 Blood Biochemistry: At V1 and V7: Sodium, potassium, chloride, glucose, BUN, creatinine, bicarbonate, calcium, total bilirubin, AST, ALT, alkaline phosphatase, uric acid, total cholesterol, HDL, LDL. At V3, V4 and V5: sodium, potassium, chloride, glucose, BUN, creatinine

5 Coagulation: PT, PTT, INR.

6 Urinalysis - Specific Gravity, pH, glucose, protein, ketones, blood.

7 EDSS-Expanded Disability Status Scale.

8 MSFC including T25FW and 9-HPT

9 Symbol Digit Modality Test (SDMT).

10 12 item MS Walking Scale (MSWS-12).

11 An Early Termination (ET) visit will be conducted only for participants who discontinue the study after the first treatment, post Visit 3. The ET visit will include all the procedures required at study Visit 7.

BrainStorm Cell Therapeutics Ltd.
Statistical Analysis Plan - Protocol BCT-101-US

April 12, 2019

Table 3: Detailed Schedule of Assessments for Cell Transplantation Visits (V3, V4, and V5)

Estimated Time	xx:00-yy:00	12:00	14:00	20:00	08:00	12:00
Time\ Procedure	Up to 8 hours before transplant	Hr. 0	Hr. 2 (\pm 15 minutes)	Hr. 8 (\pm 15 minutes)	Hr. 20 (\pm 30 minutes)	Discharge/up to Hr. 24
Admit to In-patient Facility	✓					
Physical Examination	✓					✓
Concomitant medication review	✓					✓
Hematology ³	✓					
Blood biochemistry ⁴	✓					
Coagulation ⁵	✓					
Blood collection for biomarkers	✓				✓	
Vital signs ²	✓		✓	✓	✓	✓
Adverse events review ⁶	✓		✓	✓	✓	✓
Cell Transplant IT		✓				
Retention of CSF sample		✓				
Visual inspection of injection site			✓		✓	
Discharge from Inpatient Setting						✓

Abbreviations: BUN = blood urea nitrogen, CSF = cerebrospinal fluid, INR = international normalized ration, IT = intrathecal, PT = prothrombin time, PTT = partial thromboplastin time

*Hematology, biochemistry and coagulation labs are to be drawn and checked before transplant

**To be determined for each study site

1. Hematology: Complete blood count (red blood cells with indices, white blood cells with differential and Platelet count, hemoglobin, hematocrit)
3. Sodium, potassium, chloride, glucose, BUN, creatinine
4. Coagulation - PT, PTT, INR
5. Pulse rate, Blood pressure (Respiratory rate, Body temperature)

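### No pregnancy test is scheduled before any of the three intrathecal doses; the latest one is nominally 6-10, 14-18 and 22-26 weeks old when they are given

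*Protocol*

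**What the plan says.** Pregnancy bars entry: exclusion 13 in protocol section 3.2 lists "Pregnant women or women currently breastfeeding", judged during screening. Inclusion 7 in section 3.1 sets the test times: "Women must be willing to undergo a serum pregnancy test at screening, and at the conclusion of the study". It also requires surgical sterility or agreement not to become pregnant, and medically approved contraception during the study and for at least 3 months after the last transplantation.

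The visit lists match. Section 4.6.1 (Visit 1) has "Blood collection for a serum pregnancy test (Female participants of childbearing potential"), and section 4.8.3 (Visit 7, Week 28) has "Blood collection for a serum pregnancy test (Female participants"). In the schedules (protocol Appendix 1, Table 1, and SAP section 4.5, Table 2) the row "Pregnancy test (for women with childbearing potential") carries two check marks. An early termination visit repeats the Visit 7 procedures and so includes a test.

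At the dosing visits, protocol sections 4.7.1, 4.7.3 and 4.7.5 list the assessments made up to 8 hours before transplant. Blood is drawn for hematology, coagulation, a short chemistry panel and biomarkers, and "Hematology, coagulation and chemistry lab results will be reviewed prior to the lumbar puncture". No pregnancy test is listed. Protocol Table 2 and SAP Table 3, "Detailed Schedule of Assessments for Cell Transplantation Visits (V3, V4, and V5"), have no row for one. Section 4.4 names hCG among the safety tests but refers to the schedule tables for timing, so it adds none.

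**The concern.** The protocol treats pregnancy as incompatible with entry and requires contraception beyond the last dose, yet it checks pregnancy status only at screening, weeks before exposure begins, and again after exposure has ended. A woman who conceives after screening despite contraception could receive one or more doses before the pregnancy is recognised.

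The protocol is stricter about other results that go out of date. Viral tests must be repeated if the bone marrow aspiration falls more than 7 days after screening (section 4.4), and hematology, coagulation and chemistry are redrawn before every lumbar puncture. No similar rule covers pregnancy. Nor do sections 8.2 and 8.3 name pregnancy as a reason to stop or withhold treatment, although the general safety and discretion clauses in 8.2 would allow stopping.

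What is at stake is participant and fetal safety in a trial whose primary objective is safety. No endpoint, analysis population or inference depends on it.

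**Working it through.** **Inputs**

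- Screening to bone marrow aspiration: 1-4 weeks (protocol section 2.2).
- Aspiration to dose 1: 5-6 weeks (section 4.7.1).
- Screening to dose 1 as stated: 6-10 weeks (synopsis and section 2.1).
- Doses at Day 0, Week 8 and Week 16. The window is ±14 days, counted from the first transplantation in sections 4.7.3 and 4.7.5 but applied to each interval in section 2.1.
- Visit 7 at Week 28, ±5 days.

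**The plan's own interval.** 1 + 5 = 6 weeks and 4 + 6 = 10 weeks, which reproduces the stated 6-10 weeks.

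**Age of the latest test at each dose** = (6 to 10 weeks) + nominal week of the dose

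| Dose | Nominal | With ±14 days |
|---|---|---|
| 1 (Week 0) | 6-10 weeks | none stated |
| 2 (Week 8) | 14-18 weeks | 6 + 8 − 2 = 12 to 10 + 8 + 2 = 20 weeks |
| 3 (Week 16), window from Visit 3 | 22-26 weeks | 6 + 16 − 2 = 20 to 10 + 16 + 2 = 28 weeks |
| 3 (Week 16), window on each interval | 22-26 weeks | 6 + 16 − 4 = 18 to 10 + 16 + 4 = 30 weeks |

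Footnote 12 to protocol Table 1 allows wider windows for manufacturing reasons, so the ages can be greater.

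**Gap between the two scheduled tests.** (6 to 10) + 28 = 34-38 weeks nominally, for a participant who reaches Visit 7. All three doses fall inside it.

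**With a test at each dosing visit.** The test would be at most 8 hours old at each dose. Nominal gaps between tests would be 6-10 weeks (Visit 1 to 3), 8 weeks (3 to 4), 8 weeks (4 to 5) and 28 − 16 = 12 weeks (5 to 7), so the longest is 12 weeks. Scheduled tests per woman rise from 2 to 5. The ceiling on extra tests is 3 × 20 = 60, reached only if every participant were a woman of childbearing potential.

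**The case against.** The strongest objection is that test age does not measure harm. A conception soon after screening would probably be recognised well before dose 3, so a 26-week-old test is not clearly worse than a 10-week-old one. That is right, and the ages should not be read as a rising risk. The exposure of concern is a recent, unrecognised conception before any of the three doses.

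The second objection is that several safeguards already exist: contraception (with a barrier method added for sexually active users of oral contraceptives), physical examination and adverse event review before each dose, investigator discretion to discontinue, and pregnancy reporting within 24 hours. These do shrink the residual risk. But contraception does not reveal its own failure, and the reporting clock starts only once the pregnancy is known. None of the measures is designed to find an unrecognised pregnancy on the day of dosing.

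Third, the documents show no fetal hazard from the product, the Investigator's Brochure is not available here, and with 20 participants of both sexes aged 18 to 65 the number of women affected may be small. This stands as a limit on how strongly the point can be put: it is a precaution.

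Finally, participants who leave early are tested at the early termination visit. That is true, but it is not a dosing visit and does not change the finding.

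**Conclusion.** The concern holds. No pregnancy test is scheduled at or near any dose, and the latest one is nominally 6-10, 14-18 and 22-26 weeks old at doses 1, 2 and 3. The ages rest on the protocol's nominal intervals; the windows widen the ranges for doses 2 and 3 as shown above. No risk figure is offered, because the documents give neither the number of women of childbearing potential nor a contraceptive failure rate.

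The omission is a consistent design choice, and the screening test properly serves the entry criterion. It should be changed because the remedy is small and would carry the entry bar on pregnancy through to the time of exposure.

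**What to change.** For women of childbearing potential:

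1. Add a pregnancy test to the pre-transplant assessments at Visits 3, 4 and 5 (protocol sections 4.7.1, 4.7.3 and 4.7.5, and Tables 1 and 2), with matching changes to SAP Tables 2 and 3. Use serum hCG on the blood already drawn, or a rapid urine test where serum turnaround could exceed the product's shelf life.
2. Require a negative result before the lumbar puncture, alongside the laboratory results already reviewed then.
3. State in sections 8.2 and 8.3 that after a positive result the dose is withheld and no further dose is given during the pregnancy, with reporting under 7.3 and safety follow-up under 4.9.
4. Amend inclusion 7 to name three test occasions: screening, before each transplantation, and the end of the study.

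A further test before cell preparation is optional. Section 2.4 says "About 2 weeks prior to each treatment, MSC will be thawed, propagated and induced into MSC-NTF cells", so it would fall at about Weeks −2, 6 and 14. It could avoid preparing a dose that cannot be used, but those weeks match no scheduled visit or call, so it needs an extra sample. It does not replace the test on the day.

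**Cost.** Three tests per woman, at most 60 in all, plus a protocol amendment and a short consent change. Under section 11 the local laboratory already runs the serum test, and the by-subject listing in SAP section 8.9 can take the results. There are two real drawbacks. The result must be back within the 8-hour pre-transplant period and the product's shelf life, whose length is not given. A positive result on the day also means discarding a prepared autologous dose (section 12.4).

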3.2. EXCLUSION CRITERIA

Study participants meeting any of the following criteria during screening evaluations will be excluded from entry into the study:

1. Prior stem cell therapy of any kind.
2. Active participation in any other MS interventional study or use of unapproved MS investigational therapy within 90 days prior to the Screening Visit (Visit 1).
3. Inability to lie flat for the duration of intrathecal cell transplantation and/or bone marrow aspiration, or inability to tolerate study procedures for any other reason.
4. History of clinically significant autoimmune disease (excluding thyroid disease) that may confound study results in the opinion of the Investigator and the medical monitor,

Brainstorm Cell Therapeutics Ltd.	IND#018615	
Phase 2 Clinical Protocol BCT-101-US Amendment 1.1, June 2019	MSC-NTF cells (NurOwn®)	Page 25 of 59

myelodysplastic or myeloproliferative disorder, leukemia or lymphoma, whole body irradiation, hip fracture, or severe scoliosis.

5. Any unstable clinically significant medical condition other than MS (e.g., within six months of Visit 1, had myocardial infarction, angina pectoris, and/or congestive heart failure), any clinically significant coagulopathy, treatment with anticoagulants that, in the opinion of the Investigator, would compromise the safety of the participants.
6. Any history of malignancy, within the previous 5 years, with the exception of non-melanoma localized skin cancers (with no evidence of metastasis, significant invasion, or re-occurrence within three years of the Screening Visit (Visit 1)).
7. Serum aspartate aminotransferase (AST) or alanine aminotransferase (ALT) value >3.0 times the upper normal limit.
8. Serum creatinine value >2.0 times the upper normal limit.
9. Positive test for Hepatitis B (HBV; surface antigen (HBsAg) and antibodies to core antigen (IgG and IgM anti-HBc)), Hepatitis C (HCV), or human immunodeficiency virus (HIV) 1 and 2.
10. Current use of immunosuppressant medication or use of such medication within 6 months of study enrollment (aside from Rituximab or other approved B-cell immunotherapy). Alemtuzumab (Lemtrada), Cladribine (NDA submitted), Natalizumab (Tysabri), S1P modulators (Gilenya) are excluded for safety reasons due to the known risk of systemic autoimmune disease, malignancy, opportunistic infections, and cardiovascular toxicity associated with these therapies, as well as theoretical effects on MSC-NTF cell homing and migration, that may be associated with Natalizumab and/or S1P modulators (Gilenya).
11. Any history of acquired or inherited immune deficiency syndrome.
12. Any history of either substance abuse within the past year, or unstable psychiatric disease according to the Investigator's judgment.
13. Pregnant women or women currently breastfeeding.
14. Subjects for whom MRI is contraindicated (i.e., have a pacemaker or other metallic implanted device, or are unable to remain in the machine for period of time needed to acquire a scan).

